12 PROTOCOL VIOLATIONS

A protocol violation occurs when the participant or the study investigator fails to adhere to significant protocol requirements affecting the inclusion, exclusion, participant safety and primary endpoint criteria. Protocol violations for this study include, but are not limited to, the following:

- Failure to meet inclusion/exclusion criteria
- Use of a prohibited concomitant medication

Failure to comply with Good Clinical Practice (GCP) guidelines will also result in a protocol violation. The Principal Investigator will determine if a protocol violation will result in withdrawal of a participant.

When a protocol violation occurs, it will be discussed with the investigator and a Protocol Violation Form detailing the violation will be generated. A copy of the form will be filed in the site's regulatory binder and in the Sponsor's files.

13 DATA SAFETY MONITORING

The study will require 48-hour reporting by sites of all laboratory values, signs/symptoms, and SAEs. The study will have intensive Phase I safety monitoring, which will include regular and frequent team review (every week for the first 2 months of the study; then every two weeks thereafter) of all reported events. In addition, for any Grade 3 or 4 events, sites will be instructed to contact the study team by email.

Safety monitoring will include team review of adverse events (including all reported signs/symptoms, laboratory abnormalities, diagnoses, and SAEs) and team assessment as to the possible relationship of adverse events to the study treatment. The review will also include assessment any participants with an unconfirmed CD4+ T cell or HIV RNA measurement indicating a potential safety endpoint. Regular team monitoring will also assess early study discontinuations and visit/sample completeness. In addition, study accrual and baseline characteristics of study participants will be reviewed periodically during accrual. After a dose cohort has completed accrual and sufficient follow-up time is available, the team will evaluate whether to dose-escalate and open the next dose cohort to accrual, as described below.

Safety Monitoring Committee (SMC). We have established an independent Safety Monitoring Committee (SMC) for this study. As safety concerns for kansui pertain primarily to gastrointestinal symptoms (expected to be mild) and perhaps control of HIV infection, these areas are represented on the SMC by well-recognized experts: [name] (Professor of Medicine, University of Utah, expert in epidemiology, infectious disease, HIV, and clinical research), [name] (Assistant Professor of Medicine, UCSF, expert in clinical gastroenterology), [name] (Professor of Medicine, UCSF, and an expert in complementary medicine) and [name] (Associate Professor of Medicine, UCSF, and expert on HIV management and clinical trials).

The committee will be co-chaired by [name] at the University of Utah and [name] at UCSF, who both have experience in the regulatory aspects of clinical trials and will independently deliberate using study data.

The SMC will meet after completion of each dose cohort to review safety data. The meeting will occur no earlier than two weeks after the last dose. The decision to move to the next dose cohort will be made by the SMC, after consultation with the study investigators.

A study data coordinator will produce administrative reports regularly describing study progress including the following: (1) accrual, (2) demographics, (3) study subject status, (4) laboratory data, and (5) number and type of serious AEs. Reviews will be communicated to the University of Utah and UCSF Committee on Human Research (CHR), study sponsor, and/or federal agencies, as appropriate. The SMC will have access to treatment assignment. The study will be discontinued if the SMC determines that it is in the best interest of the subjects.

Grade 1 or 2 AEs will not result in any change to the study plans. If there is evidence for a Grade 3 AE that is not caused by the study drug, the study will continue as planned. On

the other hand, Grade 3 AEs thought to be possibly caused by the intervention and any Grade 4 AEs will result in a hold on any future enrollments until a decision to proceed or to stop the study is made by the SMC

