PLANNED INTERIM ANALYSES	During the study, safety will be monitored by a Safety Monitoring Committee (SMC), which will be led by an HIV specialist. The SMC will review all study procedures before the initiation of the study. They will have the full and final authority to stop the study for any safety concern at any point. Given the unknown safety profile of Euphorbia kansui , the first participant in each dosing level will complete 5 days of study prior to any further participants commencing the study. The decision to proceed with further drug administration will be taken by the Principal Investigators, taking into consideration clinical and laboratory adverse events. The decision to proceed with the next dosing level will be taken by the SMC. Specifically, dosing will be stopped and the SMC will be notified if one Grade 4 or two Grade 3 drug related adverse events or laboratory abnormalities are reported, if a participant develops virologic failure (defined as any HIV-1 RNA levels >200 copies/mL or a single HIV-1 RNA level >1000 copies/mL), becomes pregnant or initiates breastfeeding, or is required to initiate one of the prohibited concomitant medications listed in section 7.1. If stopping/pausing criteria are not met, the remainder of the dosing cohort will be enrolled/dosed the subsequent week. The study will proceed to the next dosing level provided the

	stopping/pausing criteria are not met. A University of Utah Department of Medicine faculty member who is not otherwise involved in the study and who will not communicate with the study investigators regarding any aspect of the SMC reports will prepare the monitoring reports. The SMC will review accrual, adverse events summaries, CD4+ T-cell counts and HIV RNA levels/suppression over time, off-study rates and completeness of follow-up, by dose cohort.

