10.3 Monitoring

During the study, safety will be monitored by a Safety Monitoring Committee (SMC), which will be led by a qualified University of Utah faculty member in the Department of Medicine with expertise in HIV clinical research (see Section 13 below). The SMC will review all study procedures before the initiation of the study. They will have the full and final authority to stop the study for any safety concern at any point. The Principal Investigator at the University of Utah will be the primary medical monitor responsible for study adverse event monitoring and will report adverse events and unanticipated problems to the University of Utah IRB and the SMC. All participants will be followed for possible adverse events and unanticipated problems throughout the study period.

Participants will be monitored in an outpatient clinic during the first 4-6 hours post-dose on dosing days. At each visit, participants will be assessed for any new symptoms, and a study coordinator will obtain vital signs. The study will require 48-hour reporting of all laboratory values, signs/symptoms, and serious adverse events (SAEs). The study will have intensive Phase I safety monitoring, which will include regular and frequent team review (every week for the first 2 months of the study; then every two weeks thereafter) of all reported events. In addition, for any Grade 3 or 4 events, sites will be instructed to contact the study team by email.

- Grade 1 or 2 Toxicity: Participants who develop a Grade 1 or 2 AE or toxicity may continue study treatment. If a participant chooses to discontinue study treatment, the site should notify the kansui protocol core team as noted above, and encourage the participant to complete any remaining study visits.
- Grade 3 or 4 Toxicity: Participants experiencing Grade 3 or 4 AEs requiring permanent discontinuation of study treatment should be followed closely for resolution of the AE to Grade ≤ 2 and the protocol core team must be notified. Participants discontinuing study treatment should be encouraged to complete any remaining study visits.

[name] will be contacted directly to report medical concerns or questions regarding safety.

[contact]

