10.4 Criteria for Discontinuation

Safety will be monitored by the dedicated SMC, led by a qualified HIV specialist in the University of Utah Department of Medicine (see Section 13 below). The SMC will have full and final authority to stop the study at any point for safety concerns. Given the unknown safety profile of *Euphorbia kansui*, the first participant in each dosing level will complete 5 days of study prior to any further participants commencing the study. The decision to proceed with further drug administration will be taken by the Principal Investigator, taking into consideration clinical and laboratory adverse events. The decision to proceed with the next dosing level will be taken by the SMC. Specifically, dosing will be paused and the SMC will be consulted if one Grade 4 or two Grade 3 drug related adverse events or laboratory abnormalities are reported.

In addition, since there is currently insufficient data demonstrating the effect of kansui on antiretroviral therapy or other concomitant medications (and vice versa), we will evaluate serum HIV-1 RNA levels using standard clinical assays within each dosing cohort prior to dose escalation. HIV RNA measures will be collected on the initial dosing day(s) (Day 1 for Cohort 1, Days 1-3 and 102-104 for Cohort 2), at the 24-hour post dosing follow-up visits on Day 2 (for Cohort 1) and Days 4 and 105 (for Cohort 2), and on Day 31 and 132. This is to safeguard against the potential risk of virologic failure and/or the development of resistance due to sub-therapeutic antiretroviral therapy drug levels in study participants.

Specifically, safety discontinuation criteria will include:

1. Any serious adverse event assessed as at least possibly related to study treatment:
 - a. Any Grade 4 drug-related adverse event or laboratory abnormality
 - b. Two Grade 3 drug-related adverse event or laboratory abnormality
2. Virologic failure (defined as any two consecutive HIV-1 RNA levels >200 copies/mL or a single HIV-1 RNA level >1000 copies/mL). These values would be above the levels predicted to be seen with HIV reactivation with most current latent reactivating agents and are safety stopping criteria currently used for other HIV latent reactivating agent trials, e.g., the AIDS Clinical Trials Group (ACTG 5336) trial, evaluating the role of Sirolimus on immune activation and the latent reservoir in chronic HIV-infected, ART-suppressed individuals.
3. Pregnancy or breastfeeding

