4. Requirement for prohibited concomitant medications (see section 7.1)
5. Clinical reasons believed life threatening by the physician, even if not addressed in the toxicity section of the protocol

The specific adverse events that will be solicited include: diarrhea, gastrointestinal irritability, gastrointestinal bleeding, headache, and symptoms of dehydration (light-

headedness, tachycardia). For the most likely expected reported adverse event, diarrhea, we will strictly adhere to established toxicity grading used by the National Cancer Institute for chemotherapy-induced diarrhea.^{39,40}

Grade	Description
1	Increase of fewer than four stools per day over baseline
2	Increase of four to six stools per day over baseline
3	Increase of seven or more stools per day over baseline; incontinence; hospitalization indicated
4	Life-threatening consequences; urgent intervention indicated
5	Death

** Based on information from National Cancer Institute, 2010.*

If stopping/pausing criteria are not met, the remainder of the dosing cohort will be enrolled/dosed the subsequent week. The study will proceed to the next dosing level provided the stopping/pausing criteria are not met. A University of Utah Department of Medicine faculty member who is not otherwise involved in the study and who will not communicate with the study investigators regarding any aspect of the SMC reports will prepare the monitoring reports. The SMC will review accrual, adverse events summaries, CD4+ T-cell counts and HIV RNA levels/suppression over time, off-study rates and completeness of follow-up, by dose cohort.

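### One possibly related, non-serious Grade 3 event holds enrollment under section 13 but lets the cohort proceed under 10.4 and the synopsis, and no section pauses dosing of enrolled participants while the SMC decides

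*Combined protocol and SAP*

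**What the plan says.** Section 13 states that "Grade 3 AEs thought to be possibly caused by the intervention and any Grade 4 AEs will result in a hold on any future enrollments", with the hold lasting until the SMC decides whether the study proceeds or stops. It does not mention dosing of participants who are already enrolled.

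Section 10.4 sets a different threshold, which also counts laboratory abnormalities: "dosing will be paused and the SMC will be consulted if one Grade 4 or two Grade 3 drug related adverse events". The synopsis, under planned interim analyses, uses the same counts with a firmer verb: "dosing will be stopped and the SMC will be notified if one Grade 4 or two Grade 3 drug related adverse events". Both then give the same default: "If stopping/pausing criteria are not met, the remainder of the dosing cohort will be enrolled/dosed the subsequent week". Section 10.4 also says: "The decision to proceed with further drug administration will be taken by the Principal Investigator".

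Three other provisions bear on the point.

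- The discontinuation list in 10.4 opens with "Any serious adverse event assessed as at least possibly related to study treatment", but its only sub-items are any Grade 4 event and two Grade 3 events.
- Section 10.3 says: "Participants experiencing Grade 3 or 4 AEs requiring permanent discontinuation of study treatment should be followed closely". It does not say which Grade 3 events require discontinuation.
- Section 9.2.7 limits mandatory dose interruption to toxicities attributable to kansui.

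**The concern.** Section 13 treats a possibly related Grade 3 event as serious enough to need an SMC decision on whether the study goes on. Section 10.4 and the synopsis treat the same single event as below threshold and tell the site to continue with the cohort. They also differ on who decides: the SMC in section 13, the Principal Investigator in 10.4.

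The second part is a gap. Even when section 13 is followed exactly, it stops only new enrollments. Cohort 2 participants take three daily doses and later cross over, so participants can be mid-course when the event occurs. Once all six are enrolled, the section 13 hold affects only replacements. The protocol itself calls the safety profile of kansui unknown and names diarrhea as the most likely event; Grade 3 diarrhea on its scale includes seven or more extra stools a day. At stake is whether participants take further doses while the committee is still considering whether anyone should.

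**Working it through.** The plan states no operating characteristics for its stopping rules, so there is no figure to reproduce. The check sets the rules side by side.

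| Event | Section 13 | Section 10.4 and synopsis | Dosing of those already enrolled |
|---|---|---|---|
| One Grade 3, unrelated | Study continues | Criteria not met | Continues |
| One Grade 3, possibly related, not serious | Enrollment held until the SMC decides | Criteria not met; rest of cohort goes ahead the next week | No pause required |
| Two Grade 3, drug related | Enrollment held | Dosing paused (10.4) or stopped (synopsis); SMC brought in | Paused or stopped |
| One Grade 4, drug related | Enrollment held | As above | Paused or stopped |

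Only the second row is in conflict, and it is also the row with no dosing rule.

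**Is the section 13 trigger one event or several?** The sentence uses a plural. The sentence before it, its direct contrast, concerns a single Grade 3 event not caused by study drug. That supports a one-event trigger.

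**Does another section fill the dosing gap?** Section 10.3 covers follow-up after permanent discontinuation but sets no interim hold. The serious-event item in 10.4 may catch a single related Grade 3 event that is also serious, although its sub-items point the other way, so the point is limited to non-serious events. The separate triggers (virologic failure, pregnancy or breastfeeding, need for a prohibited medication, a reason the physician judges life threatening) apply only if they occur.

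**Illustration of exposure (timing assumed).** The documents give no SMC decision time. Section 4.1 has participants start on separate days, and 10.4 has them follow in the week after the sentinel.

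- Same participant: an event after dose 1 leaves 3 − 1 = 2 doses in that course; after dose 2, 3 − 2 = 1.
- Five non-sentinel participants starting on days 1 to 5 (assumed): doses per day are 1, 2, 3, 3, 3, 2, 1, total 15, kansui or placebo. With an event after the day 1 dose and a decision taking 2, 3 or 7 days (assumed), the doses due first are 2 + 3 = 5; 5 + 3 = 8; and 8 + 3 + 2 + 1 = 14.
- One start per week, on days 1, 8, 15, 22 and 29 (assumed): the counts are 2, 2 and 2 + 1 = 3.
- All these counts suppose that nobody uses discretion to stop.

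**Illustration of frequency (event risk assumed).** If each of six participants independently has probability p of a related Grade 3 event, counting at most one each, the chance that exactly one is affected is 6p(1 − p)^5. For p = 0.05, 0.10, 0.20 and 0.30 this gives 0.232, 0.354, 0.393 and 0.303. These values of p are not from the documents.

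**The case against.** The strongest reply is that the rules can be applied together: hold enrollment at one related Grade 3 event, and pause dosing at two Grade 3 or one Grade 4. The next-week instruction is conditional, and a section 13 hold could be read as one of the pausing criteria it refers to. This is a sensible way to run the study, but the text does not say it: 10.4 and the synopsis define their own criteria without mentioning section 13. Nor would it close the dosing gap.

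A second reply is that real safeguards exist. The first participant at each dose level completes 5 days before others begin, which in Cohort 2 covers all three doses and the Day 4 visit, although that participant may be on placebo. Each dosing day opens with adverse event review, a targeted examination, vital signs and blood tests. Participants are monitored for 4 to 6 hours after dosing, and sites email the study team about any Grade 3 or 4 event. The investigator may stop a participant, and the SMC, which has access to treatment assignment, may stop the study at any time. All of this stands and makes harm less likely, but none of it is a required pause while the SMC decides.

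Three stronger readings are not supported.

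- A reader might infer that staff could follow either section and comply. Enrolling during a section 13 hold would breach section 13.
- A reader might infer from "The study will require 48-hour reporting by sites of all laboratory values, signs/symptoms, and SAEs" that the site would not know of an event before doses 2 and 3. That is a limit on reporting; the pre-dose review can reveal the event earlier.
- A reader might infer that participants screened before the sentinel's first dose escape the hold. Section 4.1 places enrollment after eligibility, and 10.4 bars others from commencing until the sentinel's 5 days are complete.

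**Conclusion.** The point holds for one narrow case: a single Grade 3 event or laboratory abnormality, at least possibly related, not serious, and meeting no other discontinuation criterion. For that event the sections disagree on whether the cohort goes ahead, and none requires dosing of enrolled participants to wait for the SMC.

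The conclusion rests on the wording and on reading section 13 as a one-event trigger. It does not depend on the illustrative counts. Those range from 2 to 14 further doses according to assumed start dates and decision times, and they do not give the chance of any such dose. It would be wrong to infer that the trial lacks stopping rules: drug-related Grade 4 events and pairs of drug-related Grade 3 events do pause or stop dosing. The change is worth making because the case is foreseeable and the edit is small.

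**What to change.** 1. In 10.4 and the synopsis, make the instruction to enroll or dose the rest of the cohort the next week subject to no section 13 hold being in force.
2. In section 13, for a Grade 3 or Grade 4 event at least possibly related to study treatment, extend the hold to remaining study dosing, kansui or placebo, until an expedited SMC decision. Keep the existing enrollment hold for any Grade 4 event. Do not pause dosing for unrelated Grade 4 events, since 9.2.7 and 10.4 tie dosing action to attributable toxicity. Keep one Grade 4 or two Grade 3 drug-related events as the discontinuation criterion.
3. Let the SMC decide whether an interrupted 3-day course is restarted or the participant is replaced under 11.3.

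The drafting cost is a few clauses. The operational cost is a possible short delay and an occasional interrupted course. With consecutive-day starts (assumed), unfinished courses after each day's doses number 1, 2, 2, 2, 2, 1, 0, so at most two of the six participants would be interrupted. Each replacement would add one participant's screening, visits and samples.

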14 STATISTICAL METHODS AND CONSIDERATIONS

14.1 Data Sets Analyzed

[name] will be performing the data analysis for the study. Paired analyses using Wilcoxon signed rank tests will be performed to evaluate whether there is a statistically significant change in markers of immune activation (CD69, CD38, and/or HLA-DR) on CD4+ and CD8+ T cells after a 1, 2, or 3 doses of *Euphorbia kansui* extract powder prepared as tea compared to baseline (reference will be the average of the three baseline measures). Multivariate analyses will then be performed to evaluate the association between kansui and measures of immune activation at post-dosing, using linear mixed effects models, which account for within-participant correlation of observations and allows for greater stability in the estimate of the outcome measures within individuals. Similarly, for measures of the HIV reservoir, we will perform linear mixed effects regression to compare CA-US RNA levels before and after kansui and use negative binomial mixed effects regression (a method to analyze over-dispersed count data) to compare plasma HIV RNA levels before and after kansui administration (reference will be the average of three baseline measures).

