STATISTICS Primary Analysis Plan	[name] has expertise in epidemiology and biostatistics. She will be performing the data analysis for the study. Paired analyses using Wilcoxon signed rank tests will be performed to evaluate whether there is a statistically significant change in markers of immune activation (CD69, CD38, and/or HLA-DR) on CD4+ and CD8+ T cells after a 1 or 3 doses of Euphorbia kansui extract powder prepared as tea. Multivariate analyses will then be performed to evaluate the association between kansui and measures of immune activation at post-dosing, using linear mixed effects models, which account for within-participant correlation of observations and allows for greater stability in the estimate of the outcome measures within individuals. Similarly, for measures of the HIV reservoir, we will perform negative binomial mixed effects regression (a method to analyze over-dispersed count data) to compare the size of the latent HIV reservoir before and after kansui administration.
Rationale for Number of Participants	A total of 8 participants (2 from dosing cohort 1 and 6 from dosing cohort 2) will contribute to the analysis, with 8 or 25 timepoint measures, respectively. The within-individual variability will be reduced by use of the within-individual control measures, as well as the repeated measurements post-dosing. The primary outcome of the study will be an increase in the % T cell activation (CD38+ HLA-DR+) of CD8+ and CD4+ T cells. Based on our recent experience performing a phase 1 trial of canakinumab (an interleukin-1 beta inhibitor) to reduce inflammation in chronic HIV-infected ART-suppressed individuals, ¹ we estimate that we will have 80% power to detect a within-individual increase of 2.7 points in the % CD8+ T cell activation (standard deviation [SD] at 31 days of 1.6%). We will also assess virologic changes as secondary outcomes in the study. Based on data from our recent HIV latency phase 2b trial of disulfiram, ² we estimate that we will have 80% power to detect 0.6-0.7 log increases in cell-associated unsPLICED (CA-US) HIV RNA (SD=0.4 and 0.5 for Day 4 and Day 31, respectively), and a 0.6-0.5 log increases in ultra-sensitive plasma HIV RNA (SD=0.4 and 0.3 for Day 4 and Day 31, respectively).

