14.4 Analysis of Secondary Endpoints

We will perform Wilcoxon rank sum tests to compare levels of immune activation (CD69, CD38, and/or HLA-DR expression on CD4+ and CD8+ T cells) between dosing cohorts and Wilcoxon signed rank tests to compare measures within individuals. We will perform linear mixed effects modeling to compare the effect of *Euphorbia kansui* extract powder prepared as tea on immune activation over time and account for repeated measures within individuals, compared to pre-treatment (using the average of three baseline measures). Similarly, we will perform linear mixed effects regression modeling to assess changes in CA-US RNA levels and use negative binomial mixed effects

modeling to changes in plasma HIV RNA levels, before and after kansui administration (the reference will be the average of three baseline measures).

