14.5 Sample Size

A total of 8 participants (2 in dosing cohort 1 and 6 in dosing cohort 2) will contribute to the analysis, with 8 or 25 timepoint measures, respectively. The within-individual variability will be reduced by repeated measurements post-dose. Based on existing data from our study population regarding the percent CD38+HLA-DR+ CD4+ T cells (standard deviation of 4.9%) in our study population and a paired, one sample, repeated measures analysis, we will have greater than 80% power to detect a 2.7% change in CD4+ T cell activation levels post-dose. Similarly, we will have greater than 80% power to detect a 17% change in cell-associated HIV-1 RNA and a 0.37% change in plasma HIV-1 RNA.

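### CA-US HIV RNA has two conflicting models, and neither the synopsis nor Section 14 says that the linear one is fitted on the log scale used for the synopsis power statement

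*Combined protocol and SAP*

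**What the plan says.** The synopsis (Primary Analysis Plan) states that "for measures of the HIV reservoir, we will perform negative binomial mixed effects regression". It makes no split by assay, and the synopsis lists cell-associated and plasma HIV RNA together as the reservoir measures.

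Section 14.1 assigns a different model to the cell-associated measure: "we will perform linear mixed effects regression to compare CA-US RNA levels before and after kansui". Section 14.4 repeats it: "we will perform linear mixed effects regression modeling to assess changes in CA-US RNA levels". Both sections keep negative binomial regression for plasma HIV RNA only. Neither mentions a transformation, a random-effects structure or a rule for undetectable values.

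The synopsis (Rationale for Number of Participants) sizes the outcome in log units, claiming "80% power to detect 0.6-0.7 log increases in cell-associated unsPLICED (CA-US) HIV RNA", with "SD=0.4 and 0.5 for Day 4 and Day 31, respectively". The base of the log is not given. Section 14.5 uses another unit: "we will have greater than 80% power to detect a 17% change in cell-associated HIV-1 RNA", with no SD.

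**The concern.** The two models answer different questions. A linear model of untransformed levels estimates an absolute difference. A negative binomial model with its usual log link estimates a ratio of means. With both in the plan, the choice can be made after the data are seen.

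The second issue is scale. An effect expressed in log units is a fold change. Section 4.1 justifies the crossover by significant differences between individuals in baseline virologic values. If everyone has the same fold rise, the absolute rise is proportional to baseline. As an illustration, a four-fold rise adds 300 copies to a baseline of 100 and 3,000 copies to a baseline of 1,000. On the untransformed scale the high-reservoir participants therefore drive both the estimate and its variance, and the power claimed in the synopsis need not apply.

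**Working it through.** **Inputs.** From the synopsis: effects of 0.6 log (Day 4) and 0.7 log (Day 31), SD 0.4 and 0.5, 80% power. From Section 14.5: 8 participants, of whom 6 are in Cohort 2, a paired one-sample approach, and the 17% figure. Assumed, because the documents are silent: two-sided alpha 0.05, the SD read as that of the within-person change, log base 10 (natural log as an alternative), and a between-person baseline SD of 0.3-0.7 log.

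**1. Reproduce the plan's figure.** Paired t test, noncentrality = effect / SD × √n, critical value t(0.975, 5) = 2.571 for n=6.
- Effect detectable with 80% power: 0.574 at SD 0.4 and 0.717 at SD 0.5. These round to the printed 0.6 and 0.7.
- Power at the printed effects: 0.6/0.4 × √6 = 3.67 gives 83%; 0.7/0.5 × √6 = 3.43 gives 78%.
- With n=8 the detectable effects would be 0.46 and 0.58, which do not match.

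So the synopsis figure is that of a log-scale paired analysis in the six Cohort 2 participants.

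**2. Same data, untransformed.** Simulation with 200,000 trials per setting: log baseline drawn with the assumed SD, log change drawn as N(0.6, 0.4) or N(0.7, 0.5), both back-transformed, then a paired t test on the absolute change. Log10 units, n=6:

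| Baseline SD (log10) | Power, 0.6 / SD 0.4 | Power, 0.7 / SD 0.5 | Median share of largest participant |
|---|---|---|---|
| 0 | 46.4% | 33.2% | 43%, 47% |
| 0.3 | 32.5% | 24.5% | 47%, 50% |
| 0.5 | 19.8% | 15.7% | 53%, 56% |
| 0.7 | 11.7% | 9.6% | 60%, 62% |

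The last column is the share of the summed absolute changes, for the two effects in turn. On the log scale power stays at 83% and 78% whatever the baseline spread. With all 8 participants (0.6 / SD 0.4, baseline SD 0.3-0.7), power falls from 95% to 21-53%.

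**3. Natural logs.** For 0.6 / SD 0.4, n=6, untransformed power is 67%, 58% and 47% at baseline SD 0.3, 0.5 and 0.7, against 83% on the log scale.

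**4. Random intercept only.** Two sets of simulations with several pre- and post-dose values per person gave 74-96% and 78-97% rejection on the raw scale. In the second set (300 replicates, participant effects approximated as fixed, assumed residual SD 0.25 log10), false positives under no effect were 12-18% raw and 19-23% log. A model without a person-level treatment effect treats repeated values as independent evidence about the change.

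**5. Negative binomial.** A rough check (log link, participant fixed effects, 300 replicates, some non-convergence) rejected in about 99-100% of trials when the effect was present and in about 20-30% when it was not. There was no power loss of the kind in step 2.

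**6. Section 14.5.** log10(1.17) = 0.068. At SD 0.4 the noncentrality is 0.068/0.4 × √6 = 0.42 for n=6 and 0.48 for n=8, giving power of about 6% and 7%. In natural logs, ln(1.17) = 0.157, with power of about 12% (n=6) and 16% (n=8). On neither base does it match a claim of more than 80%.

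**The case against.** The strongest reply is that silence is not error. Section 14 says levels, which is the documents' general word for these measures, and the only SDs given for this outcome are in log units. A log-scale linear model may well be what was meant. That stands: the documents do not show that an untransformed analysis is planned, only that the scale is unstated.

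A reader might infer that both models depart from the log scale and share the dominance problem. The documents do not support this. Negative binomial regression ordinarily uses a log link and works on ratios; there the problem is the contradiction with Section 14.

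A reader might also infer that most of the power will be lost. That needs untransformed values, person-level change as the error term, base-10 logs and a sizeable baseline spread together. The documents fix none of these, and a random-intercept-only model would keep 74-97% on the raw scale. That is little comfort given its false-positive rate, which taking logs alone does not cure.

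Finally, the stakes are limited. CA-US RNA is a secondary endpoint, Section 5.1 disclaims a primary efficacy endpoint, and Sections 14.1 and 14.4 agree with each other.

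**Conclusion.** The point holds as a conflict of models and an unstated scale for a secondary endpoint. The synopsis and Section 14 name different models for CA-US RNA, and neither names the log scale on which the synopsis power figure rests.

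The size is conditional. With an untransformed linear analysis, person-level change as the error term, log10 units, two-sided alpha 0.05 and a baseline SD of 0.3-0.7 log10, power with six participants drops from about 78-83% to about 10-32%, and one participant typically supplies 47-62% of the total absolute change. With natural logs the fall at 0.6 / SD 0.4 is from 83% to 47-67%. With a random intercept only, the greater risk is false positives. Separately, the 17% figure in Section 14.5 cannot be reconciled with the synopsis sizing.

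**What to change.** In the synopsis, Section 14.1 and Section 14.4, specify log10 CA-US RNA as the outcome of one linear mixed model that includes a person-level random treatment effect. A paired participant-level summary on the log10 scale would serve equally. Report the geometric mean fold change with its 95% CI. State that negative binomial regression applies to plasma HIV RNA only. Restate Section 14.5 in the same log10 units, with the SD, alpha and number of participants used.

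The cost is wording, with no added visits, samples or participants. The one small downside is that a convention for undetectable values must be fixed before logs are taken. The change should be made before the Cohort 2 data are unblinded.
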